**Table 3: Surgical and equipment adverse events in DBS, based on 3 sources. The percentage per patient is given.**

Information source	Reference 1 (n=133)	Reference 2 (n=124)	Reference 3 (n=468)

Lead fracture	6%	3%	0.4%
Intraoperative electrode migration	1.5%		
Late postoperative electrode migration	1.5%		
Implanted pulse generator migration	1.5%	4%	
Erosion	2.3%	3.2%	0.4%
Infection	1.5%	1.6%	1.3%
Erosion plus infection	1.5%		
Frequent external interference	1.5%		
Other		8.9%	0.02%
TOTAL	17.3%	17.7%	2.3%

Reference 1. Blomstedt P, Hariz MI. (2005). Hardware-related complications of deep brain stimulation: a ten year experience. *Acta Neurochir (Wien)*. 147:1061-4.

Reference 2. Schuepbach WM, et al. (2013) Neurostimulation for Parkinson's disease with early motor complications. *N Engl J Med*. 368: 610-22.

Reference 3. Experience of functional neurosurgery group ([name], [name], [name]) at the University of Miami (unpublished)

Safety will not primarily be evaluated statistically.

In addition to the continual monitoring of adverse events, safety analyses will use generalized linear models. The main dependent variable of interest is the Numeric Rating Scale (NRS) score for pain. Additionally there will be a fairly large number of dependent variables derived from assessments of other symptoms. Distributions will be modeled as binomial (yes=1 or no=0) or multinomial (e.g., score =1, 2, or 0) or normal (e.g., heart rate peak power after tilt, quantitative sensory thresholds). Less frequently, a Poisson distribution will be appropriate (e.g., number of times the patient reports autonomic dysreflexia in a given period). An appropriate link function will be chosen for each assumed distribution. Covariates to be considered are injury level, injury completeness and electrode configuration. The hypotheses to be tested for any variable (using the above factor coding) is that  $B \succ A$ ,  $C \succ B$ ,  $D \succ B$  and  $D \succ C$ . Marginal means can be used for this (except in multinomial examples, when main effects must suffice). Some participants may lack data from one condition (if they immediately opted for continuous high-level stimulation after the initial untreated period). If the continuous treatment is stopped soon after it starts, only the placebo effect ( $A \succ B$ ) will be available. Representative independent variables from each type of symptom will be further explored by discriminant analysis, which can confirm that one or more treatment condition represents a distinct state in the multivariate outcome space.

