### 12.3 Treatment Groups

One (1) Treatment group. All participants will receive the same treatment (long-term DBS in PAG/PVG) and undergo the same procedural protocol. Ethical considerations forbid a control group that receives implant surgery without stimulation. Hence participants must serve as their own controls.

After internalization of the pulse generator (electronic stimulator) and subcutaneous tunneling of connecting cables to the electrode and 12-48 hours for recovery from this internalization procedure, stimulation will be applied to the patient. The patient will be asked to report their ongoing pain level, on a 0-10 numerical rating scale (NRS) with the stimulation turned off and, for each electrode contact, in small voltage steps up to the threshold for any aversive effects (if not seen in the first step). Floating, dizzy or warm feelings can be expected, based on literature reports. If there is no ongoing pain, cutaneous brushing to cause allodynia below the injury, at sensitive sites determined in the pre-surgical testing sessions, will be used. Blood pressure will also be measured by cuff before and during electrical stimulation. This will be repeated on week 12. The optimal level will be 67% of threshold for aversive or other unwanted effects (e.g. motor) or device maximum (10 V) if such effects are not observed. We expect the optimal voltage to be 4-10V. A frequency range of 10-20 Hz and pulse width range of 250-450  $\mu$ s is anticipated, but these parameters will be set according to the subject's responses. The subject returns home with the optimal stimulation settings after each programming session.

Subjects will receive monthly adjustment of stimulation levels to optimize analgesia on the NRS. They will be given the option of remaining in the study if any level becomes unpleasant in later months.

The subject will be given up to 4 different program groups after study week 16, differing in contacts, voltages, frequencies and pulse widths, all determined to be without adverse effect by the clinician programmer in the in-person office session. The subject is asked to switch program groups using their patient programmer. They switch immediately if relief is unsatisfactory, and stay with the best program for pain relief, or with any adequate program if the best is not determined, keeping a pain diary (score 0-10) at intervals of 24 hours or less to help determine the best program group.

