**Table 2. Flow sheet of Visits/Assessments**

Study Visit Schedule for the initial 52-week study period:

week ( $\pm 7$ days) >>	<<No of tests	1	2	3, 5	4, 6	5, 6	7	8	9, 11, 13, 15, 17, 19	10, 14, 18	12, 16	20, 32	21, 23, 25, 27, 29, 31, 33, 35, 37, 39, 41, 43, 45, 47, 49, 51	22, 26, 28, 30, 34, 36, 38, 42, 44, 46, 50	24, 40, 48	52
SCREENING		x														
SURGERY, or week-5,6 screening for surgery						x	x	x								
LONG-TERM DBS in PAG/PVG (note 1)									x	x	x	x	x	x	x	x
TAPERING or STOPPING of PAIN MEDICATION(S)												x			x	
COMPREHENSIVE TESTING	4		x										x			x
ABBREVIATED TESTING	5										x				x	
TELEPHONIC INTERVIEW	40			x	x				x	x			x	x		
Sites																
Miami VA Medical Center (note 2)		x	x								x	x			x	x
Miami Project in Lois Pope Life Center (note 2)				x	x				x	x	x	x	x	x	x	x
University of Miami Hospital						x	x	x								
Study Therapy																
Targeting and lead placement	1						x									
DBS and lead connection	1							x								
DBS adjustment &-or sensing / possible 5 minute inactivation	9							x			x	x			x	x
General Assessments																
Informed Consent	3	#1	#2				#3									
Spinal Cord Injury history/Demographics	1	x														
Medical history, Brief medical examination	1	x														
Drug Abuse Screening Test (DAST)	1	x														
Folstein Mini-Mental State Examination (MMSE)	4	x											x			x
Beck Depression Inventory (BDI)	9	x									x	x			x	x
(PGIC)	44								x	x	x	x	x	x	x	x
Adverse Event assessment	52		x				x	x	x	x	x	x	x	x	x	x
Vital signs (BP, SpO2, temp)	12	x	x				x	x			x	x			x	x
Patient Diary on Medications	50	x	x	x	x				x	x	x	x	x	x	x	x
Qualitative exit interview	1															x
Neuro System Exams																
ASIA Neurological Exam	4	x											x			x
Tilt table response exam (note 3)	4		x										x			x
Patient Self-assessment of Autonomic Responses	38			x	x				x	x			x	x		
Autonomic Standards Assessment	9		x								x	x			x	x
Multidimensional Pain Inventory (MPI-SCI)	4		x										x			x
Quantitative sensory testing (QST)/Allodynia	4		x										x			x
ISCI Pain Basic Data Set / NPSI	25		x		x					x	x	x		x	x	x
Imaging																
Neuroimaging - MRI study	1						x									
Neuroimaging - CT study	1							x								
Electro-cardiogram (EKG)	1						x									
Chest x-ray	1						x									
Laboratory																
CBC, Comprehensive Metabolic Panel (including Mg + , Renal & Liver Function), PT/PTT	2		x					x								

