#### 14.5 Post Implantation Procedures & Follow-up

Procedures performed to evaluate the safety of the investigational procedures and to evaluate subject outcome for this study include:

- A. Beginning one week after surgery, participants will undergo follow-up assessments post-implantation:
  - i. Pain assessments every 2 weeks (ISCI basic pain data set, NPSI), starting on week 10, will assess for development of, or changes in neuropathic pain; more comprehensive pain testing (MPI quantitative sensory testing/allodynia) will take place on comprehensive testing visit weeks (20-week, 32-week, and 52-week).
  - ii. Autonomic Standards Assessment: on on-site visit weeks (BP, HR, sympathetic skin response) and on week 20, week 32, and week 52 (Tilt table response exam). Patient Self-assessment of Autonomic Responses occurs weekly starting on week 3, except on on-site visit weeks.
  - iii. QoL assessments: on on-site visit weeks, starting on week 12 (Beck Depression Inventory (BDI-1a)) and weekly, starting on week 9 (Guy/Farrar Patient Global Impression of Change (PGIC));
  - iv. ASIA motor and sensory assessments: on weeks 20, 32 and 52 to assess any improvement or deterioration in neurological function;
  - v. a qualitative exit interview with audio recording at 52 weeks, giving subject and investigators will be given the opportunity for open comments and questions concerning elements of the study.

- B. Follow-up assessments will take place either at the Miami VA Hospital or at The Miami Project to Cure Paralysis, Department of Neurological Surgery, for regular follow-up visits for 44 weeks post-surgery. At each visit, information will be collected regarding the safety of the treatment, the presence or absence of adverse side effects, and the efficacy of the therapy with respect to recovery of neurological functioning or the development of adverse effects.

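### Section 17.1 plans tests with generalized linear models but names no participant term, although each of 12 participants contributes 9 to 25 repeated pain scores

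*Combined protocol and SAP*

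**What the plan says.** The text after Table 3 in section 17.1 states that "safety analyses will use generalized linear models" and that "The main dependent variable of interest is the Numeric Rating Scale (NRS) score for pain". Outcomes are to be modelled as binomial, multinomial or normal, each with a suitable link. Less often "a Poisson distribution will be appropriate (e.g., number of times the patient reports autonomic dysreflexia in a given period").

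On model terms it says: "Covariates to be considered are injury level, injury completeness and electrode configuration". Tests are then introduced with "The hypotheses to be tested for any variable (using the above factor coding"), followed by four ordered comparisons among conditions A to D, using marginal means where possible. No A–D coding appears above that sentence or elsewhere in the current text.

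Section 12.3 explains that a control group is ruled out: "Hence participants must serve as their own controls". Section 17.3 relies on the same feature when it argues that 12 participants are enough.

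Pain is scored often. Section 14.5 plans "Pain assessments every 2 weeks (ISCI basic pain data set, NPSI), starting on week 10", and the Table 2 row "ISCI Pain Basic Data Set / NPSI" gives 25 as the number of tests. The opening of section 17.1 refers to pain intensity at routine visits and to within-subject differences. Nothing in section 17 names a participant factor, random effect, generalized estimating equation, repeated-measures structure or robust variance. The time-series analysis in section 12.5 concerns stimulation levels, not these scores.

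**The concern.** An ordinary generalized linear model assumes independent rows. Scores from one person are correlated, so the pooled residual is the wrong yardstick for both kinds of effect in the plan.

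- Injury level and completeness are properties of the person, as is electrode configuration if it means unilateral or bilateral leads. They are informed by 12 people, not by every score.
- Condition contrasts are made within a person. Without a participant term the stable differences between people stay in the error, and differences in how people respond are ignored.

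The count outcome has a similar problem. Section 7.1 describes dysreflexia that may be triggered several times a day, while section 13.3 does not require it for entry, so rates should differ widely between participants. A plain Poisson model has no room for that.

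At stake are the p-values and any intervals for the main variable in a study meant to inform whether a larger one is warranted. An analyst choosing the correlation structure after seeing the data could also change which results look significant.

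**Working it through.** **Inputs from the documents.** 12 participants (section 17.1). ISCI/NPSI assessments in Table 2 at week 2 (1); 4, 6 (2); 10, 14, 18 (3); 12, 16 (2); 20, 32 (2); 22, 26, 28, 30, 34, 36, 38, 42, 44, 46, 50 (11); 24, 40, 48 (3); and 52 (1). On-site follow-up at weeks 12, 16, 20, 24, 32, 40, 48 and 52 (section 15).

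**Reproducing the plan's count.** 1 + 2 + 3 + 2 + 2 + 11 + 3 + 1 = 25, as Table 2 states: 3 before surgery and 22 after. That gives 12 × 25 = 300 rows. Restricting to the week 2 baseline and the eight later visits gives 9 scores and 12 × 9 = 108 rows.

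**Assumptions.** The documents give no within-person correlation (ICC); 0.3–0.7 is used. They give no spread of individual response; an SD of change of 0 to 2 points is used, with a total score variance of 4. Tests are two-sided at 0.05.

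**Participant-level covariates.** With constant correlation ρ and m scores per person, the true standard error exceeds the pooled one by about √(1 + (m − 1)ρ). False-positive rates are from simulation with two groups of six.

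| ICC | 25 scores: factor | False positives | 9 scores: factor | False positives |
|---|---|---|---|---|
| 0.3 | √8.2 = 2.86 | 51% | √3.4 = 1.84 | 30% |
| 0.5 | √13.0 = 3.61 | 60% | √5.0 = 2.24 | 40% |
| 0.7 | √17.8 = 4.22 | 67% | √6.6 = 2.57 | 48% |

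A normal approximation agrees: at 25 scores and ICC 0.5, 2{1 − Φ(1.96/3.61)} = 0.587. The 300 rows are then worth 300/13.0 = 23 independent ones. Any positive ρ makes the factor exceed 1.

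**Condition contrasts.** Because A–D are undefined, before versus after implant is used as a stand-in.

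- *Uniform response.* The true standard error is about √(1 − ρ) of the pooled one: 0.84, 0.71 and 0.55 at ICC 0.3, 0.5 and 0.7. For 3 v 22 scores the exact ratios are 0.86, 0.74 and 0.58, and the pooled test rejects a true null in 2.3%, 1.1% and 0.3% of trials. It is too cautious, so power is lost.
- *Response varying between people, 3 v 22 scores, ICC 0.5.* Rejection is about 1%, 2%, 6%, 11% and 15% at SD of change 0, 0.5, 1, 1.5 and 2 points. Separate simulations put the last figure at up to 17%.
- *Response varying, 1 v 8 scores.* Rejection stays between 0.2% and 5% for SD 0–2 and ICC 0.3–0.7, so there is no inflation.
- *Serial correlation of 0.5–0.9 per two weeks, 3 v 22 scores.* The true standard error is 1.38–1.60 times the pooled one, so the pooled test is anticonservative.
- *One paired difference per participant.* In the constant-correlation settings, with or without varying response, this holds about 5%.

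**Counts.** No episode rate or spread is given, so no size is claimed. Stable differences between people are enough to mislead the covariate effects. For condition contrasts the damage comes from people changing by different amounts.

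**The case against.** The strongest reply is that this is a 12-person, single-arm, open-label phase 1 study. Section 17.1 calls the safety analysis mainly descriptive and not primarily statistical, and section 17.3 says that only descriptive analysis is proposed. No success criterion, stopping rule or sample size rests on these p-values. This stands, and it limits the severity. It does not remove the point, because section 17.1 still lists hypotheses to be tested and section 17.3 claims adequate power for many planned tests.

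Three stronger readings are tempting, and the documents do not support them.

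- *That the plan has chosen a model which excludes participants.* The text is silent. It speaks of within-subject differences and own controls, and allows for participants lacking data from one condition. This is an omission, not a stated exclusion.
- *That the covariates will come out significant by default.* The listed hypotheses are condition contrasts; the covariates are only to be considered. The 50–67% applies if their effects are tested or reported, and a six-versus-six split is itself an assumption.
- *That the error always runs in both directions.* The sign for condition contrasts depends on response variation, serial correlation and the number of scores. At moderate variation the errors nearly cancel.

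It is also fair that 25 is the largest count available. Section 17.1 refers to routine visits, and the documents do not say outright that the modelled pain score is the ISCI item. Outcomes such as tilt response and quantitative sensory testing have only 4 tests each. The covariate problem shrinks with fewer scores but does not vanish.

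**Conclusion.** The concern holds as a specification gap that should be fixed. Section 17.1 is detailed enough to be run, apart from the missing A–D coding, and run literally it ignores the repeated scores and the pairing on which the design depends.

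The firmest part is that standard errors for participant-level covariates are too small at any positive within-person correlation: by a factor of 2.9–4.2 with 25 scores and 1.8–2.6 with 9, at an assumed ICC of 0.3–0.7. The condition-contrast result is conditional: too cautious if response is uniform, anticonservative with 3 v 22 scores if response varies widely or scores are serially correlated, and not inflated by varying response with 1 v 8. The ICC, the response SD and the before/after stand-in are assumptions. The descriptive label keeps this below a critical defect.

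**What to change.** In section 17.1:

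1. Replace generalized linear models with generalized linear mixed models that have a participant random intercept and a participant-by-condition effect. For normal outcomes, state small-sample degrees of freedom such as Kenward–Roger.
2. State how serial correlation will be checked and what is done if it is present. The random effects above do not by themselves deal with it.
3. For dysreflexia counts, use a negative binomial or quasi-Poisson model with a participant effect.
4. Assess injury level, completeness and electrode configuration on 12 participant-level values only, and say whether electrode configuration means the number of leads or the active contacts, which can change between programming sessions.
5. Restore the A–D coding, and say which pain scores enter the model (all 25, or baseline and routine visits). No contrast can be run without the coding.

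A simple alternative for any single contrast is one paired difference per participant between the two conditions. It is not equivalent to the full model: collapsing to one before and one after mean would lose the separate B, C and D comparisons and would average across the medication reduction from week 20.

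The cost is about a paragraph of wording and a little more analysis work with standard software. Some intervals will widen. With 12 participants the richer random-effects models may not always fit, so the paired difference should be named in advance as the fallback.

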Autonomic functioning after SCI depends on the injury level. Visceral efferents are damaged directly by mid-thoracic or sacral injuries. Higher control of autonomic function is degraded after cervical or high thoracic SCI, when only vagal control remains. Autonomic dysreflexia (AD) is a frequent consequence of cervical or high thoracic injuries. It mostly occurs when the lesion is above the 6th thoracic segment. Its estimated frequency is 48-90% in patients with tetraplegia or high quadriplegia [24-26]. AD is a cluster of symptoms caused by a massive sympathetic outflow, which includes elevated blood pressure, headache, flushing, sweating above the lesion level and abnormal heart rhythms. It is typically provoked by activity in visceral or cutaneous afferents below the injury. Distension of bladder or colon, such as occurs from loss of control of evacuation, may precipitate AD. It can occur sporadically, triggered several times each day, but sometimes it lasts for many days, since the patient is generally unaware of aggravating stimuli below the injury level.

Various categories of antihypertensive agents are used for symptomatic control of AD, in particular nitrates (e.g., topical nitroglycerin), calcium blockers (e.g., nifedipine) and selective alpha-adrenergic antagonists (e.g., prazosin, terazosin) [27]. In the short-term, these treatments are generally adequate. However, because AD can present as an acute crisis, long-term treatment with an effective blocking dose is poorly matched to the breakthrough of symptoms and their chronic sequelae. Alpha-adrenergics, for example, in addition to their adverse acute effects and contraindications, produce receptor upregulation with long-term use. Additional problems are specific to SCI. Norepinephrine facilitates movement generation in the spinal cord and is a transmitter at sphincter muscles of hollow organs. Blockade of its principal alpha-1 receptors can therefore exacerbate functional deficits in SCI.

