### 13.3 Inclusion Criteria

- a) Age: 22 - 60 years old at last birthday;
- b) Diagnosis of traumatic SCI at or above the 12th thoracic segment (T12) that occurred >365 days;
- c) Neuropathic pain below the level of injury, as determined based on pain in an area with neurological deficit and described as burning, shooting, electric, stinging etc.

- d) The injury must have occurred at least 1 year prior to entering the study and participants must have experienced chronic pain for a minimum of six months.
- e) The disability must have a grade on the American Spinal Injury Association Impairment Scale (AIS) of ASIA-A, ASIA-B, ASIA-C or ASIA-D as determined by qualified examiners.
- f) Pain (neuropathic) of moderate severity or greater is present, when the patient is taking their routine pain medication, with a score of at least 4 on a numerical rating scale (range of 0 to 10).
- g) Participants who are on medications for other conditions, such as diabetes, will be considered as candidates for this study. The dose will be monitored throughout the trial. (They will be excluded if the drug is being used to treat epilepsy, Parkinson's diseases, or other brain degenerative diseases.)
- h) Participants will be allowed to utilize over-the-counter drugs such as NSAIDs, acetaminophen and aspirin. Their use will be documented in the weekly pain assessments. A list of "allowed" medications will be provided to study participants. After the surgery, patients will be allowed to take stay on the protocol if they take Tramadol (50-100 mg, 2 times a day for up to 2 weeks) as a rescue drug in addition to their stable medication.
- i) The patient must be taking pain medication to maintain a stable level of medication from 4 weeks before surgery to 12 weeks after (the primary endpoint), except on the day of surgery. On the day of the surgery, in the presence of a physician who can provide immediate backup pain control if needed, medications will be stopped until the acute effects of DBS on analgesia have been evaluated.
- j) The participant must be willing to comply with the protocol including all scheduled visits.
- k) Autonomic dysreflexia can be present but is not a necessary requirement. Autonomic dysreflexia will be defined as rise of systolic pressure by more than 30 mm Hg during noxious skin stimulation or when the bladder or bowel are full, or apparently spontaneously over a period of minutes
- l) Literate at 8th grade level or above.

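### Autonomic dysreflexia counts are to be fitted with a plain Poisson model that allows for neither overdispersion nor repeated reports, so their standard errors are likely too small

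*Combined protocol and SAP*

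**What the plan says.** In the text after Table 3, Section 17.1 states that "safety analyses will use generalized linear models" and assigns a distribution to each type of outcome. For counts, "a Poisson distribution will be appropriate (e.g., number of times the patient reports autonomic dysreflexia in a given period". The only choice left open is the link: "An appropriate link function will be chosen for each assumed distribution". The covariates listed are injury level, injury completeness and electrode configuration. No participant term, dispersion parameter or robust variance is named.

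The same paragraph sets out contrasts to be tested: "The hypotheses to be tested for any variable (using the above factor coding") is followed by comparisons among levels A to D, which are not defined anywhere. It also foresees that some participants will have no data for one condition.

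On the outcome itself, Section 7.1 says of dysreflexia: "It can occur sporadically, triggered several times each day, but sometimes it lasts for many days". It explains the long duration by the patient's usual unawareness of the stimulus. Section 13.3 adds: "Autonomic dysreflexia can be present but is not a necessary requirement". Section 14.5 sets the reporting schedule: "Patient Self-assessment of Autonomic Responses occurs weekly starting on week 3, except on on-site visit weeks".

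**The concern.** A Poisson model fixes the variance of a count at its mean, which corresponds to independent episodes at a constant rate. A participant whose unnoticed trigger persists for days, and who has quiet weeks otherwise, will produce weekly counts that vary more than that. Adding a participant term does not remove this, because the excess variation lies between weeks within the same person.

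If the excess is ignored, the interval for the change in episode rate is too narrow, and chance runs of good or bad weeks can look like benefit or harm. Relief of dysreflexia is part of the primary objective in the synopsis, and cumulative change in autonomic symptoms is part of Aim 4 (Section 11.1). Over-precise evidence on the count could therefore colour the judgement on whether a larger study is warranted.

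**Working it through.** **Inputs from the documents.** At most 12 participants, each their own control. In Table 2 the self-assessment row is ticked for 4 weeks before implantation (weeks 3 to 6) and for 6 + 3 + 16 + 11 = 36 weeks afterwards. The table's own total is 38, which would leave 34 afterwards. The difference does not matter here.

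**Assumptions.** The documents give no episode rate, dispersion or significance level for this outcome, so there is no figure of the plan's own to reproduce. I take a two-sided 5% level, a comparison of weeks before with weeks after implantation (levels A to D being undefined), and one episode count per week.

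**Closed form.** If the within-participant variance is φ times the mean, the true standard error is √φ times the Poisson one. The actual error rate of a nominal 5% test is 2 × [1 − Φ(1.96/√φ)], and the interval on the log scale has 1/√φ of its proper width.

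| φ | 1.96/√φ | Actual error rate | Interval width relative to correct |
|---|---|---|---|
| 1 | 1.960 | 5% | 100% |
| 1.5 | 1.600 | 11% | 82% |
| 2 | 1.386 | 17% | 71% |
| 4 | 0.980 | 33% | 50% |
| 8 | 0.693 | 49% | 35% |

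**Simulation check.** 12 participants, 4 against 34 weeks, no effect of stimulation, 6,000 runs per case, weekly negative binomial counts with φ = 1 + mean × k.

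| Mean per week | k | φ | Closed form | Simulated Poisson rejection |
|---|---|---|---|---|
| 3 | 0 | 1 | 5.0% | 5.2% |
| 0.5 | 0.5 | 1.25 | 8.0% | 7.4% |
| 3 | 0.25 | 1.75 | 13.8% | 13.4% |
| 3 | 0.5 | 2.5 | 21.5% | 21.2% |
| 3 | 1 | 4 | 32.7% | 32.7% |
| 14 | 0.5 | 8 | 48.8% | 49.0% |

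The two agree. A participant effect leaves the simulated values unchanged. If the rate shifts for a whole period instead of week by week, Poisson rejection at a mean of 3 is 44% (k = 0.25) and 57% (k = 0.5).

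**What does not inflate the error.** Differences between participants alone (k = 1), with complete data, give 4.8%. If 3 of the 12 lack the pre-implant condition, the same differences give 31% without a participant effect and 4.8% with one.

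**How the alternatives behave with no effect of stimulation.**

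- Dispersion-scaled Poisson: about 5% when the excess is week to week, but 13% to 27% when bouts last 2 to 4 weeks and 32% to 38% when they last a whole period.
- Paired t test on each participant's square-root rate: 5% to 7% at 3 or more episodes a week, 8.5% at 0.5 a week, and about 10% to 13% with bouts of 2 to 4 weeks.
- Variance clustered by participant: about 14% to 25% with 6 participants and 9% to 15% with 12.

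**The case against.** The strongest reply is that nothing hangs on this test. Section 17.1 opens by calling the safety analyses mainly descriptive, the text under Table 3 says that safety is not primarily a statistical evaluation, and Section 17.3 proposes only descriptive analyses. The count is a single example among less frequent cases, and pain on the numerical rating scale is the main variable. The self-reported count is absent from the efficacy parameters in Section 16 and from the synopsis secondary outcomes. This largely stands and limits the consequence. It does not remove the point: the same section lists hypotheses to be tested for any variable, Section 17.3 speaks of sufficient power for many planned tests, and a Poisson interval is too narrow even if no p-value is reported.

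A reader might infer more: that the protocol itself calls the episodes clustered, so that the test rejects for clustering and not for stimulation. The documents do not support that. The word appears in Section 7.1 only for symptoms ("AD is a cluster of symptoms caused by a massive sympathetic outflow"), and dysreflexia lasting many days could be counted as one long episode. Overdispersion is a fair inference from that text, but its size is unknown.

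Nor does the concern reach Aim 3, which is about stimulus-evoked or persistent hypertension and not this count. The before-and-after comparison used here is also a construction, since levels A to D are undefined and no section says that the weekly self-assessment records a number of episodes.

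**Conclusion.** The concern holds in a limited form. The plan names a plain Poisson model for repeated dysreflexia reports, makes no provision for excess variance or for the participant, and describes the condition in a way that makes the Poisson variance unlikely. Standard errors and intervals for the episode rate ratio are therefore likely too small. With an assumed variance-to-mean ratio of 1.5 to 8, the error rate of a nominal 5% test is about 11% to 49%, and higher if bouts run over several weeks. These figures rest on assumed dispersions and on a before-and-after comparison of weekly counts. The consequence is over-precise evidence on a secondary count. The documents do not support the view that the trial's conclusion would be wrong.

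**What to change.** In Section 17.1, replace the plain Poisson model for dysreflexia counts with the following:

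- **Main summary:** a within-person comparison of weekly episode rates before and after implantation, with the number of reported weeks as denominator, each participant's two rates shown, and small-sample paired inference. State what counts as one episode.
- **Supporting model:** negative binomial, or Poisson with an estimated dispersion, with a participant effect and an offset for reported weeks. Say that neither fully corrects for bouts lasting several weeks. The paired comparison also keeps some excess error in that case.
- **Not to be relied on:** cluster-robust variance with 12 or fewer participants.
- **Population:** keep all participants in the safety summary, so that dysreflexia first appearing after implantation is counted. Treat those with dysreflexia at baseline as a subgroup for the change in rate.

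The cost is a short paragraph of text and wider intervals. For the dispersion-scaled model they widen by √φ on the log scale, which is 1.2-fold at a ratio of 1.5 and 2.8-fold at a ratio of 8.
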